11.1.1 Mayo score

Mayo score will be calculated as the sum of the four sub-scores. If any of the four sub-scores are missing, total Mayo score will be missing. Mayo score ranges from 0-12, with higher scores indicating a more severe disease.

11.1.2 Partial Mayo score

Partial Mayo score will be calculated as the sum of the scoring from the three sub-score areas: stool frequency, rectal bleeding and the physician's global assessment. If any of the sub-scores are missing, partial Mayo score will be missing. Partial Mayo score ranges from 0-9, with higher scores indicating a more severe disease.

11.1.3 Clinical response at Week 8 based on Mayo score, the primary variable

A patient will be classified as a responder if the three criteria below are fulfilled at Week 8:

- Decrease in total Mayo score from baseline ≥ 3 points

- Decrease in total Mayo score from baseline $\geq 30\%$
- Decrease in the sub-score for rectal bleeding ≥ 1 or absolute sub-score for rectal bleeding of 0 or 1 point.

A patient discontinuing IP, requiring intensified therapy, or who underwent a colectomy or ostomy before week 8, or who have a missing Mayo score registration at week 8, will be classified as a non-responder.

11.1.4 Clinical remission at week 8 based on Mayo score

A patient will be classified as being in clinical remission if both the criteria below are fulfilled at week 8:

- Absolute Mayo score ≤ 2
- No individual subscore > 1

A patient discontinuing IP, requiring intensified therapy, or who underwent a colectomy or ostomy before week 8, or who has a missing Mayo score registration at week 8, will be classified as in no remission.

11.1.5 Mucosal healing at week 8

Mucosal healing is defined as an improvement of the endoscopy sub-score (from the Mayo score) at week 8 from 3 or 2 to ≤ 1 point, or from 1 to 0 points.

A patient discontinuing IP, requiring intensified therapy, or who underwent a colectomy or ostomy before week 8, or who has missing endoscopy sub-score registration at week 8, will be classified as not have had mucosal healing.

11.1.6 Change from baseline in Mayo score

Change from baseline to week 8 in total Mayo score will be calculated as the score at week 8 minus the score at baseline. No imputation of missing values will be performed.

11.1.7 Change from baseline in partial Mayo score

Partial Mayo score will be assessed at week 4, 8, 12, 16, 20 and 24. Change from baseline to each assessment in partial Mayo score will be calculated as the score at the assessment minus the score at baseline. No imputation of missing values will be performed.

11.2 Calculation or derivation of safety variable(s)

Baseline is defined as the most recent measurement obtained before administration of IP. In most cases this will be data from randomisation visit (Visit 2), but if no such value exists, most recent value prior to Visit 2 will be used. Change from baseline will be calculated as the visit value minus the value at baseline. BMI will be calculated from height and weight.

11.2.1 Other significant adverse events (OAE)

During the evaluation of the AE data, an AstraZeneca medically qualified expert will review the list of AEs that were not reported as SAEs and DAEs. Based on the expert's judgement, significant adverse events of particular clinical importance may, after consultation with the Global Patient Safety Physician, be considered OAEs and reported as such in the Clinical Study Report. A similar review of laboratory/vital signs/ECG data will be performed for identification of OAEs.

Examples of these are marked haematological and other laboratory abnormalities, and certain events that lead to intervention (other than those already classified as serious), dose reduction or significant additional treatment.

11.3 Calculation or derivation of pharmacokinetic variables

The pharmacokinetic (PK) analyses will be performed at MedImmune Ltd. The actual sampling times will be used in the PK calculations. PK parameters will be determined using standard non-compartmental methods. The following PK parameters will be determined:

- Areas under the time-concentration curves from zero to infinity and to last observation ($AUC_{(0-\infty)}$; $AUC_{(0-t)}$);
- Dose-normalised $AUC_{(0-\infty)}$: ($AUC_{(0-\infty)}/D$);
- Maximum observed concentration (C_{max});
- Dose-normalised C_{max} : (C_{max}/D);
- Time to C_{max} (T_{max});
- Terminal-phase elimination half-life ($t_{1/2}$);
- Apparent clearance (CL/F);
- Steady-state volume of distribution (V_{ss}/F).

Using the serum concentrations of tralokinumab, the pharmacokinetics of tralokinumab will be analyzed using the noncompartmental method as implemented in WinNonlin® Professional version 5.1 or higher.

Samples below LLOQ will be discarded from the non-compartmental analysis; a more elaborated statistical methodology will be used to handle LLOQ samples when performing population pharmacokinetic/pharmacodynamic (PK/PD) modeling.

Relationship between tralokinumab plasma concentration and effect on PD endpoints of interest (Mayo score, individual sub-scores) will be presented graphically and summarized through descriptive statistics by treatment arm (placebo vs. tralokinumab). Concentration-

effect relationships will be explored by population PK/PD analysis in NONMEM® version 6.2 or higher.

Full details of the population PK/PD analysis intended for this study will be described in a separate analysis plan. Derived PK parameters and the outcome of the PK/PD analysis may be presented in reports separate from the CSR.

12. STATISTICAL METHODS AND SAMPLE SIZE DETERMINATION BY ASTRAZENECA OR DELEGATE

12.1 Description of analysis sets

The treatment associated with a patient may differ depending on the type of analysis used for a particular analysis. The as-randomised approach and as-treated approach are defined as:

As-randomised: Each patient is assigned the patients randomised treatment i.e. the treatment associated with the randomisation code allocated to the patient, identified via the randomisation schedule.

As-treated: Each patient is assigned the patients actual treatment received the first time IP is administrated to the patient regardless of randomisation code.

12.1.1 Full analysis set

The full analysis set will include data from all randomised patients. Patients who were randomised but did not subsequently go on to receive study treatment will be included in the Full analysis set. Analyses of efficacy will be based on the full analysis set, and on the as-randomised approach.

12.1.2 Safety analysis set

The safety analysis set will include data from all patients who received at least one dose of randomised treatment and for whom any post dose data are available. Post dose data implies that there has been a contact in which there has been an opportunity to report any health problems. All safety analyses will be based on this analysis set, and on the as-treated approach.

12.2 Methods of statistical analyses

A statistical analysis plan will be prepared and finalized before clean file is declared.

Descriptive statistics for continuous data will include (but is not restricted to) n (number of values), mean, median, standard deviation, minimum and maximum value. Descriptive statistics for categorical data will include n, frequency, and percentage. These summaries will be given for placebo and tralokinumab separately.

Where appropriate, model-based point estimates will be presented together with their two-sided 95% confidence intervals. When variables are log-transformed prior to analysis, estimates and confidence intervals will first be constructed in the logarithmic scale. By taking the antilogarithms, estimates and confidence intervals for the true geometric means and ratios of true geometric means will be achieved.

To support the one-sided hypotheses of this trial, one-sided p-values will be presented in the analysis of the primary variable - clinical response at week 8, and in the analysis of the two secondary variables - mucosal healing and clinical remission at week 8. No adjustment for multiplicity will be made.

All efficacy analyses will be based on the full analysis set, safety analyses will be addressed with the safety analysis set.

12.2.1 Analysis of primary variable

The primary variable, clinical response at week 8, will be analyzed using a one-sided Cochran-Mantel-Haenszel (CMH) chi-square test, with glucocorticosteroid-refractory status as a stratification factor. The null hypothesis that the proportion of patients responding on tralokinumab is less than or equal to the proportion of patients responding on placebo will be rejected in favour of the alternative hypothesis, that the proportion of patients responding is higher on tralokinumab than on placebo, if the one-sided p-value is <0.05 .

The number and proportion of patients responding in each treatment arm will be displayed. The difference in proportions between tralokinumab and placebo will be presented using point estimate and 95% confidence intervals.

A sensitivity analysis will be performed, where patients with biopsies from affected mucosa where the central pathology assessment reported normal histology at baseline, will be excluded.

To assess the impact of premature discontinuations from IP on the primary variable, time to discontinuation of IP may be analysed using Kaplan-Mayer curves. The time to discontinuation of IP will be calculated as the date of IP discontinuation minus the date of randomization +1 day.

In addition, clinical response at week 8 will be summarized descriptively based on the following grouping variables: glucocorticosteroid-refractory status (yes or no), time since first diagnosis (≤ 5 years or > 5 years), prior immunomodulatory therapy (yes or no), and affected area in colon (rectosigmoideum involvement only, left side involvement only or extensive involvement).

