5.2.1 Procedures for randomisation

A randomisation list will be prepared using a validated computer program (GRand). Patients will be randomised to treatment with either tralokinumab or placebo in a ratio of 1:1.

Randomisation to IP will be done via an IVRS/IWRS at Visit 2. The IVRS/IWRS will sequentially allocate the treatment and provide the randomisation number and the appropriate kit ID from those available at the study site. The randomisation is carried out at the study level and the assigned randomisation numbers and the associated kit IDs will not be sequential within a study site. Forced randomisation is not allowed.

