12.2.2.2 Change from baseline in Mayo score

Depending on the distribution of the data, change from baseline to week 8 in Mayo score will be analyzed using either ANCOVA or cumulative logit methodology. Mayo score at baseline will be included as a covariate, and treatment and glucocorticosteroid-refractory status as factors in the model. Patients with no week 8 assessment and from which change from baseline cannot be calculated, will be excluded from the analysis.

Changes from baseline to all scheduled assessments in each individual subscore will be presented in shift tables.

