12.3 Determination of sample size

The sample size calculation in this study was done to demonstrate superior efficacy of 300 mg tralokinumab over placebo with regard to the primary variable, clinical response at week 8. Assuming that the true proportions of patients responding are 65% and 35% in tralokinumab and placebo respectively, and a one-sided test at $\alpha = 0.05$ with a power of 90%, this yields a planned sample size of 53 patients in each treatment arm. In total 110 patients will be randomised to yield 106 evaluable patients.

The sample size calculations were based on published data on two studies comparing 5 and 10 mg of infliximab, each to placebo, in patients with moderate to severe ulcerative colitis ([Rutgeerts et al 2005](#)). Based on the reported studies the study sponsor was given marketing authorization for infliximab in UC. Therefore an increase in the proportion of patients responding to therapy from 35% to 65% would be considered clinically relevant.

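### The CMH tests of the three week 8 binary endpoints leave out baseline Mayo score; a pre-specified baseline-adjusted analysis would be a cheap robustness gain, not the correction of an error

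*Protocol*

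**What the plan says.** Section 12.2.1 specifies a "one-sided Cochran-Mantel-Haenszel (CMH) chi-square test" for clinical response at week 8, "with glucocorticosteroid-refractory status as a stratification factor". No other stratum or covariate is named. The one sensitivity analysis excludes patients whose affected-mucosa biopsy was centrally read as normal at baseline, and baseline severity is not among the descriptive subgroup variables. Section 12.2.2.1 carries the same analysis over to mucosal healing and clinical remission. The synopsis agrees.

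The other efficacy analyses use their own baseline. For change in Mayo score, 12.2.2.2 states that "Mayo score at baseline will be included as a covariate". Sections 12.2.2.3 and 12.2.2.4 include the baseline value in the repeated-measures models, and 12.2.2.5 stratifies the Riley score test by baseline score.

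On allocation, 5.2.1 says: "Patients will be randomised to treatment with either tralokinumab or placebo in a ratio of 1:1". It describes a study-level list and gives no stratification factor. On sample size, 12.3 reads: "Assuming that the true proportions of patients responding are 65% and 35% in tralokinumab and placebo respectively" with a one-sided 5% test and 90% power, "this yields a planned sample size of 53 patients in each treatment arm"; then "In total 110 patients will be randomised to yield 106 evaluable patients".

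**The concern.** Inclusion criterion 4 requires a Mayo score of at least 6 with an endoscopy sub-score of at least 2, so every eligible patient has a baseline value at no extra cost. If that value predicts the outcome, two things follow.

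- Conditioning on it would on average sharpen the comparison.
- With about 55 patients per arm and no stated balancing, a chance difference in severity could make the primary result hard to read. Any adjustment introduced after the imbalance was seen would be open to challenge.

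The three binary endpoints, including the primary, are the efficacy comparisons for which no baseline severity term is planned.

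**Working it through.** **1. The plan's own figure.** Inputs from 12.3: 0.65 vs 0.35, one-sided alpha 0.05, power 90%.

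n = [1.645 × √(2 × 0.5 × 0.5) + 1.282 × √(0.65 × 0.35 + 0.35 × 0.65)]² / 0.30² = (1.163 + 0.864)² / 0.09 = 45.7, so 46 per arm.

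With the continuity correction, (n/4) × [1 + √(1 + 4/(n × 0.30))]² at n = 46 gives 11.5 × (1 + 1.136)² = 52.5, so 53 per arm. This matches the protocol. Without the correction, power is 93.5% at 53 per arm and 94.2% at 55.

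**2. How each endpoint depends on baseline (11.1.3 to 11.1.5).**

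| Endpoint | Fall needed |
|---|---|
| Response: larger of 3 points and 30%, on an integer score | 3 points from a baseline of 6 to 10; 4 points from 11 (3.3 rounded up) or 12 (3.6 rounded up) |
| Remission: Mayo of 2 or less | 4 points from 6; 10 points from 12 |
| Mucosal healing: endoscopy sub-score of 1 or less | 1 point from 2; 2 points from 3 |

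The hurdle changes sharply with baseline for remission and mucosal healing. For response it changes by one point, and only at the top two scores. Expressed as percentages, 3 points is 50% of 6 and 30% of 10, but it is the same fall.

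**3. Average power for response.** The protocol gives no association between baseline Mayo and response, so it is assumed here. Settings: 55 per arm, 30% refractory (odds ratio 0.6), half the patients in each of two baseline strata, placebo response 35%, one-sided 5% CMH test, 20,000 simulated trials per setting. The last column is the change found in a separate run of the same size.

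| Baseline odds ratio | Planned test, 55% vs 35% | Baseline stratum added | Change (points) | Separate run |
|---|---|---|---|---|
| 1 (not prognostic) | 69.7% | 68.7% | -1.0 | -0.9 |
| 0.5 | 68.6% | 68.7% | +0.1 | +0.4 |
| 0.33 | 68.4% | 70.5% | +2.1 | +1.8 |
| 0.25 | 68.4% | 71.8% | +3.4 | +2.9 |

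At the planned 65% vs 35% the change is about -0.5 to +1.2 points, from a starting power of about 94%.

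A second approach multiplies the variance by (1 - R²), where R² is the share of response variance explained by baseline. For R² of 0, 5%, 10% and 15%, power with 55 per arm is 94.2%, 95.2%, 96.0% and 96.8% at 65% vs 35%, and 68.2%, 70.2%, 72.2% and 74.4% at 55% vs 35%. This approximation is generous when R² is small. In direct simulation of a linearly adjusted test, R² of about 1 to 4% moved power by at most 1 point, sometimes with no gain. A clear gain appeared only at R² of about 12%: 68.4% to 73.0% at 55% vs 35%, and 94.4% to 95.9% at 65% vs 35%.

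**4. Chance imbalance.** If half the patients are severe, the difference in the severe share between arms has standard deviation √(2 × 0.25/55) = 0.095. A gap of at least 12 percentage points means at least 7 patients (7/55 = 12.7%). With a half-patient correction this is 6.5/55/0.095 = 1.24 standard deviations, or about 21% of trials, split evenly between directions. In those trials, at a baseline odds ratio of 0.5:

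- Placebo arm more severe, no true effect: the planned test rejects in about 8 to 9% of trials, and the stratified test in about 5 to 6%.
- Active arm more severe, 55% vs 35%: power is about 59% with the planned test and 67% with the stratum.

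Over all trials, type I error stays near 5% for both tests.

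**The case against.** The strongest reply is that nothing here is wrong. A CMH test with one stratum is valid under 1:1 randomisation, and leaving a covariate out of a responder test is common practice. The response variable is already defined relative to baseline. The average benefit is close to zero unless baseline is strongly prognostic, and the documents do not say that it is. At an odds ratio of 0.5 the change is within simulation error. The unseen SAP may also contain an adjusted supportive analysis. All of this stands, and it is why the point is no more than an optional improvement.

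Three stronger readings are tempting, but the documents do not support them.

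- **That the response rule itself makes baseline prognostic, because a patient at 6 must fall by 50% and one at 10 by 30%.** Both need 3 points, and the direction of any association is open.
- **That precision is demonstrably being lost on the primary endpoint.** This requires an association that no section reports.
- **That the 8 to 9% conditional error shows a biased or anti-conservative test.** It applies to one direction of imbalance only. The opposite direction pulls the error below 5%, and over randomisations the rate is nominal. Chance imbalance is random error already covered by the test and confidence interval.

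One part of the reply does not stand. The strata are fixed in 12.2.1 and the synopsis, so the choice of test has not simply been left to the SAP. Remission and mucosal healing do depend on baseline by definition, even though neither uses the 3-point and 30% rule.

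**Conclusion.** The point holds as a low-cost improvement in efficiency and robustness. The planned CMH test is valid, and 53 per arm reproduces exactly. The case for adjustment is definitional for remission (baseline Mayo) and mucosal healing (baseline endoscopy sub-score), and conditional for response.

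For response, the expected power change is about -1 to +3 points at 55% vs 35% and about -0.5 to +1 at the planned effect. These figures rest on assumed odds ratios of 1 to 0.25, an even baseline split and a 30% refractory share, none of which the protocol gives. No size can be put on the gain for remission or mucosal healing, because the protocol gives no expected rates for them. The more useful benefit is a result that can still be interpreted, without post hoc adjustment, in the roughly one trial in five with a notable severity gap.

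**What to change.** In 12.2.1 and 12.2.2.1 (or in the SAP before unblinding, if it does not already do this), pre-specify one baseline-adjusted analysis for each binary endpoint. There are two options.

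- **Add a stratum.** Stratify the CMH test by refractory status and a two-level baseline Mayo score, and give a Mantel-Haenszel risk difference over the same strata. A split at 6-8 vs 9-12 is one possibility, but the protocol offers no basis for a particular cut. This protects the primary test itself. The cost is thinner strata (four instead of two, which matters most if remission is rare) and up to about 1 point of power if baseline is not prognostic.
- **Keep the planned test and add a supportive model.** Fit a logistic regression with treatment, refractory status and baseline Mayo, using the baseline endoscopy sub-score instead for mucosal healing, and report a standardised risk difference. The primary decision rule is unchanged and loses no power, but the protection is then only supportive.

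Either option needs about a line of text and modest programming. No extra data or patients are needed.

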12.2.2 Analysis of secondary efficacy variables

12.2.2.1 Mucosal healing and clinical remission at week 8

Proportion of patients with mucosal healing and proportion of patients in clinical remission, will be analyzed and presented in the same way as the primary variable, except that no subgroup analyses will be performed.

12.2.2.2 Change from baseline in Mayo score

Depending on the distribution of the data, change from baseline to week 8 in Mayo score will be analyzed using either ANCOVA or cumulative logit methodology. Mayo score at baseline will be included as a covariate, and treatment and glucocorticosteroid-refractory status as factors in the model. Patients with no week 8 assessment and from which change from baseline cannot be calculated, will be excluded from the analysis.

Changes from baseline to all scheduled assessments in each individual subscore will be presented in shift tables.

12.2.2.3 Change from baseline in partial Mayo score

Repeated measures analysis will be used to analyze the change from baseline in partial Mayo score. The model will include treatment, glucocorticosteroid-refractory status, partial Mayo score at baseline, visit, and treatment by visit interaction as explanatory variables. The contrasts of interest are the differences at each visit between tralokinumab and placebo. Depending on the distribution of the data, partial Mayo score will be treated as either a continuous or as an ordered categorical variable.

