Following a one week enrolment period, patients will be randomised to 12 weeks double-blind treatment. Thereafter patients will enter 12 weeks follow-up off-treatment. The total length of the study is 25 weeks.

Outcome variable(s):

Primary Efficacy variable

Clinical response is defined as a decrease in Mayo score from baseline of at least 3 points and at least 30% with an accompanying decrease in the sub score for rectal bleeding of at least 1 point or absolute sub score for rectal bleeding of 0 or 1.

Secondary variables

- Change from baseline in Mayo score.
- Mucosal healing, defined as an improvement of the endoscopy subscore (from the Mayo score) from 3 or 2 to 0 or 1 point, or from 1 to 0 points.
- Change from baseline in partial Mayo score.
- Clinical remission, defined as Mayo score of 2 or lower with no individual sub-score exceeding 1 point.
- Histologic disease activity: modified Riley score.
- Markers of disease activity and intestinal leakiness in serum and faeces: CRP and albumin (in serum), calprotectin (in faeces).
- Immunogenicity: incidence of anti-drug antibodies (ADA) to tralokinumab in serum.
- Plasma pharmacokinetics (PK) parameters.
- Adverse events, safety laboratory variables, ECG, vital signs (BP, pulse, and temperature), weight, and physical examination.

Statistical methods

Primary variable, clinical response at week 8, and the secondary variables, mucosal healing and clinical remission at week 8, will be analyzed using the Cochran-Mantel-Haenszel chi-square test, stratified by glucocorticosteroid-refractory status.

Change from baseline in Mayo score and partial Mayo score will be treated as either ordered categorical variables or as continuous variables, depending on the distribution of the data. Mayo score will be analyzed using either ANCOVA or cumulative logit methodology. Partial Mayo score will be analyzed using repeated measures analysis. Repeated measures analysis will also be used to analyze change from baseline in markers of disease activity (CRP, calprotectin) and change from baseline intestinal leakiness (albumin). Modified Riley score will be compared between groups using a stratified Wilcoxon test, with baseline score as the stratification variable.

Safety variables will be presented descriptively.

All efficacy analyses will be based on the full analysis set, safety analyses will be addressed with the safety analysis set.

TABLE OF CONTENTS	PAGE
TITLE PAGE	1
PROTOCOL SYNOPSIS.....	2
TABLE OF CONTENTS.....	6

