5.8.1 Procedures for discontinuation of a patient from investigational product

A patient who decides to discontinue IP will always be asked about the reason(s) and the presence of any adverse events.

If the patient is discontinued from IP, the scheduled study visits, data collection and procedures should continue according to the study protocol until study completion. Alternatively, if the patient does not agree to this option, a modified follow up through eg,

regular telephone contacts or a contact at study completion should be arranged, if agreed to by the patient and in compliance with local data privacy laws/practices. The approach taken should be registered in the eCRF.

If a patient is withdrawn from study, see Section 5.9.

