12.2.2.4 Markers of disease activity (CRP, calprotectin) and intestinal leakiness (albumin)

Repeated measures analysis will be used to analyze the change from baseline in markers of disease activity and intestinal leakiness. The model will include treatment, baseline value, visit, and treatment by visit interaction as explanatory variables. The contrasts of interest are the differences at each visit between tralokinumab and placebo.

Markers of disease activity and intestinal leakiness will be log-transformed before analysis, unless otherwise is stated in the SAP. The number of CRP values below limit of quantification will be assessed before analysis to ensure the model appropriateness. In case of large number of values below limit of quantification another method of analysis should be considered for CRP, this method will be stated in the SAP.

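### The repeated-measures models fix one baseline slope for weeks 4 to 24, and the marker model also omits steroid-refractory status: a minor, cheaply repaired weakness of the late secondary contrasts

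*Protocol*

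**What the plan says.** Protocol section 12.2.2.3, partial Mayo score: "The model will include treatment, glucocorticosteroid-refractory status, partial Mayo score at baseline, visit, and treatment by visit interaction as explanatory variables". Section 12.2.2.4, CRP, calprotectin and albumin: "The model will include treatment, baseline value, visit, and treatment by visit interaction as explanatory variables". Both sections name the same target: "The contrasts of interest are the differences at each visit between tralokinumab and placebo".

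Section 11.1.7 sets the visits: "Partial Mayo score will be assessed at week 4, 8, 12, 16, 20 and 24". Table 8 gives the markers the same six post-baseline visits. The synopsis describes 12 weeks of treatment and then: "Thereafter patients will enter 12 weeks follow-up off-treatment". The model therefore spans three on-treatment visits (weeks 4, 8, 12) and three off-treatment visits (weeks 16, 20, 24).

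On missing data, section 11.1.7 says of partial Mayo score: "No imputation of missing values will be performed". For patients who stop investigational product, section 5.8.1 says that "the scheduled study visits, data collection and procedures should continue according to the study protocol until study completion", with telephone or similar contact as the alternative if the patient declines.

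Steroid-refractory status is a stratification factor in the primary test (12.2.1) and a factor in the Mayo change model (12.2.2.2) and the partial Mayo model (12.2.2.3). The marker model leaves it out without giving a reason. Section 5.2.1 says only: "Patients will be randomised to treatment with either tralokinumab or placebo in a ratio of 1:1". No stratification by steroid status is stated.

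**The concern.** Treatment has its own effect at each visit, but baseline has a single coefficient. The model therefore assumes that a one-point difference at baseline predicts the week-4 change and the week-24 change equally well. Over 24 weeks that include stopping the drug, this may not hold.

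If it does not, two things can follow. First, the common slope adjusts wrongly at the visits furthest from it, and those contrasts lose precision. Second, if patients go missing at different rates in the two arms in a way related to baseline, the observed arms come to differ in mean baseline at late visits. A wrong slope at that visit then leaves part of the imbalance in the treatment contrast. Partial Mayo score is not imputed, so the model alone carries the missing data.

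The late visits have a stated purpose: section 3.2.4 collects efficacy after the last dose because an asthma study suggested a prolonged effect. The missing steroid factor is a separate, smaller matter of consistency and precision.

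**Working it through.** **The plan's own figure.** The protocol gives no figure for these models. Its sample size reproduces and is not affected. For 65% v 35%, one-sided 0.05 and 90% power, n = [1.645·√(2·0.5·0.5) + 1.282·√(0.65·0.35 + 0.35·0.65)]² / 0.30² ≈ 46 per arm. With continuity correction this becomes 53, as stated in 12.3.

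**Precision, by formula.** On a standardised scale, let b_t be the true slope at visit t and β the common slope. The variance inflation is 1 + (b_t − β)²/(1 − b_t²). Suppose b falls from 0.6 at week 4 to 0.1 at week 24 (assumed), with β about 0.40-0.41:

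- Week 4: 1 + 0.20²/0.64 = 1.06.
- Week 24: 1 + 0.30²/0.99 = 1.09, or 1 + 0.31²/0.99 = 1.10. The SE ratio is √1.09 to √1.10, so visit-specific slopes cut the SE by about 4-5%.
- If b falls only from 0.5 to 0.25, the variance inflation is 1-2%.

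**Precision and bias, by simulation.** A likelihood model with unstructured covariance and six visits was fitted to large samples, with SEs rescaled to 110 patients. The true arm difference was zero. All inputs are assumptions: baseline SD 1.4, post-baseline SD 1.9 to 2.3, and slopes of change on baseline from −0.19 at week 4 to −0.51 at week 24 (moderate drift) or from 0.02 to −0.84 (strong drift). Bias is in partial Mayo points, tralokinumab minus placebo.

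| Scenario | Week-24 missing, placebo v tralokinumab | Week-24 bias, common slope | Bias/SE | Week-24 bias, visit-specific slopes | SE ratio, common/visit-specific |
|---|---|---|---|---|---|
| Moderate drift | 27% v 9% | −0.049 | 0.11 | −0.006 | 1.020 |
| Moderate drift, baseline-driven | 31% v 9% | −0.066 | 0.15 | 0.011 | 1.009 |
| Strong drift | 27% v 9% | −0.131 | 0.25 | −0.013 | 1.121 |
| Strong drift, baseline-driven | 31% v 9% | −0.201 | 0.39 | 0.001 | 1.098 |
| Strong drift, equal missingness | 18% v 18% | −0.003 | 0.01 | −0.007 | 1.121 |
| Strong drift, none missing | 0% v 0% | −0.015 | 0.03 | −0.017 | 1.115 |
| Constant slope | 29% v 10% | 0.006 | 0.02 | 0.007 | 1.000 |

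The Monte Carlo error of the bias is 0.007 to 0.014, so the last three rows show no bias attributable to the common slope. Ratios of 1.009-1.020 mean that visit-specific slopes lower the week-24 SE by 1-2%; ratios of 1.098-1.121 mean 9-11%. In the rows with bias, its sign favours tralokinumab. At 0.39 SE, a two-sided 5% test rejects with probability Φ(−1.96 + 0.39) + Φ(−1.96 − 0.39) = 0.058 + 0.009, about 6.8%.

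At week 8, in the drift scenarios, the bias was at most 0.013 points against an SE of about 0.32-0.35, and the SE ratio was at most 1.006.

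**Extreme dropout.** Take slopes falling from 0.6 to 0.1 and week-24 retention of about 53-54% on placebo against 83% on tralokinumab. The common-slope estimate is about 0.045 SD too large when dropout depends only on the previous score, and about 0.12 SD too large when it also depends on baseline. With 55 per arm, about 30 and 46 patients remain, so the unadjusted SE is √(1/30 + 1/46) = 0.24 SD. The biases are then about 0.2 and 0.5 SE. The first case shows that missingness need not depend on baseline directly: dependence on an earlier score, itself correlated with baseline, is enough when it acts more strongly in one arm.

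**Steroid factor.** For a factor of prevalence p and effect d (in SD), leaving it out multiplies the SE by √(1 + p(1 − p)d²). For p from 0.2 to 0.5:

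- d = 0.2: 1.003 to 1.005.
- d = 0.5: 1.020 to 1.031.
- d = 0.8: 1.050 to 1.077.

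In the constant-slope runs with a factor effect of 1.0 point, dropping the factor added no visible bias.

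**The case against.** A single baseline covariate with treatment by visit is a common repeated-measures model. It yields a contrast at every visit and contradicts nothing else in the protocol. A list of what a model will include does not forbid further terms, and an SAP is promised. That the baseline relation weakens is nowhere stated; off treatment, scores could move back towards baseline. Patients who stop treatment are meant to stay in follow-up, so missingness may be well below the simulated levels. The Riley score comparison (12.2.2.5) also omits the steroid factor.

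Much of this stands, and it limits the size of the point. It does not remove it. The term lists are definite, and section 12.2.2.4 leaves only the transformation and the CRP method to the SAP. Drift in either direction costs precision, since the inflation depends on the squared slope difference. Telephone contact, allowed by 5.8.1, yields no laboratory samples.

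A reader might infer more than the protocol supports:

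- That unequal dropout alone biases the late contrasts. It does not; the slope must also change over time, and missingness must be related to baseline.
- That the treatment effect will be exaggerated by some stated percentage. Any such figure rests on an assumed effect, drift and retention by arm, none of which the protocol gives.
- That omitting steroid status ignores a randomisation stratum or causes bias. No such stratum is stated, and the runs showed no bias.

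**Conclusion.** The point holds as a minor weakness confined to late secondary contrasts, which carry no multiplicity control. The facts are plain from the text: there is one baseline slope for six visits in both models, and no steroid-refractory factor in the marker model.

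The consequences are conditional. If the slope drifts, the week-24 SE is larger than it need be; the avoidable part is about 1-2% under moderate drift and 4-11% under strong drift. If missingness also differs by arm and is related to baseline, the week-24 bias is roughly 0.1-0.4 SE at about 9% v 30% missing, and up to about 0.5 SE under extreme dropout. With constant slopes or no dropout there is no bias. Week 8 is essentially unaffected, and the primary test does not use these models. The steroid omission is an inconsistency that mostly costs under 3% in SE.

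Every magnitude rests on assumed SDs, slopes and dropout. The simulations treat partial Mayo score as continuous. Its ordinal alternative and the log-scale markers were not simulated, though the same reasoning applies to the marker model.

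**What to change.** Add a baseline-by-visit interaction to the models in 12.2.2.3 and 12.2.2.4. Add glucocorticosteroid-refractory status to the marker model as a main effect, as 12.2.2.3 already does for partial Mayo score; if it is left out on purpose, say why.

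The cost is about 5 degrees of freedom for baseline by visit (six visits less one) and one for the factor. No new data are needed. Where slopes are in fact constant, little is lost: the SE ratio in the constant-slope runs was 1.00 at week 24.
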